## **5.5 Blood collection, transportation, and storage**

Blood samples will be collected from each participant during the baseline visit and the post-training visit within 24 hours. A phlebotomist will draw blood into a red-top tube (EDTA or citrate). Samples will be labeled with a study identification number. Samples to be used for safety labs will be sent to the lab by the phlebotomist. PGx samples will be stored in a 2-8°C degree refrigerator or a -

20°C degree freezer at Akron. Samples will then be transported for extraction and stored in a -80°C freezer at Gateway Biotechnology's lab.

## **6.0 EVALUABILITY**

All participants are evaluable for the primary outcome – the proportion of patients who are PTS positive as defined by the ratio of the number of participants with  $\geq 10$  dB increase in PTS to the total number of participants tested 30 days (+/- 3 days) post-shooting – provided they have had the assigned study dose and undergone post study assessments.

Participants who receive the study medication are evaluable for toxicity related to the drug. Participants are evaluated from the time of dose administration through 30 days post dose for drug related adverse events.

The participant will be withdrawn from the study if:

- Participant withdraws consent
- Investigator removes the participant from study
- The Sponsor decides to close the study

## **7.0 PHARMACEUTICAL INFORMATION**

### **7.1 Zonisamide (ZONEGRAN®)**

#### **7.1.1 Zonisamide Description**

**Molecular formula:** C8H8N2O3S

**Molecular weight:** 212.23

#### **7.1.2 Clinical Pharmacology**

The precise mechanism(s) by which ZNS exerts its antiseizure effect is unknown. ZNS may produce these effects through action at sodium and calcium channels. In vitro pharmacological studies suggest that ZNS blocks sodium channels and reduces voltage-dependent, transient inward currents (T-type Ca2+ currents), consequently stabilizing neuronal membranes and suppressing neuronal hypersynchronization. Additional information can be found in the package insert.

#### **7.1.3 Supplier**

ZNS will be supplied through Advanced Rx (Washington, PA).

#### **7.1.4 Dosage Form and Preparation**

ZONEGRAN® is commercially available for oral administration as capsules containing 25mg, 50 mg, or 100 mg of ZNS.

Each 100 mg capsule contains the labeled amount of ZNS plus the following inactive ingredients: microcrystalline cellulose, hydrogenated vegetable oil, gelatin, and titanium dioxide.

#### **7.1.5 Storage and Stability**

Store at 25°C (77°F), excursions permitted to 15–30°C (59–86°F), in a dry place and protected from light.

#### **7.1.6 Administration**

Participants will receive one time dose of oral ZNS or matching placebo. Participants will be instructed to take study drug without food. We will recommend that capsules be swallowed whole per the current approved labeling.

#### **7.1.7 Side Effects**

Potential side effects from the administration of ZNS:

- Somnolence
- Anorexia
- Dizziness
- Ataxia
- Agitation/irritability
- Difficulty with memory and/or concentration

ZNS may rarely cause serious side effects, including:

- Serious skin rash that can cause death.
- Serious allergic reactions that may affect different parts of the body.
- Less sweating and increase in body temperature (fever).
- Suicidal thoughts or actions in some people.
- Increased level of acid in blood (metabolic acidosis).
- Problems with concentration, attention, memory, thinking, speech, or language.
- Blood cell changes such as reduced red and white blood cell counts.

### **7.1 Placebo**

The placebo will contain microcrystalline cellulose which is the predominant filler in the generic capsule.

## **8.0 REGULATORY AND REPORTING REQUIREMENTS**

The entities providing oversight of safety and compliance with the protocol require reporting as outlined below. Please refer to Appendix A for definitions and Appendix B for a grid of reporting timelines.

Adverse events will be tracked for the Akron site post dose within 30 minutes, 24 hours, and at 30 days. All adverse events must be recorded on the AE tracking case report form (CRF). AEs related to study medication only will be tracked.

Reporting requirements for Washington University study team may be found in Section 8.1. Reporting requirements for secondary site study teams participating in Washington University-coordinated research may be found in Section 8.2.

In the event of a Serious Adverse Event determined by the PI to necessitate the breaking of the blind, the intervention assignment will be revealed by the independent programmer to the medical staff doctor caring for the patient. In the event the statistician is unable to be reached in a timely manner, to assure the safety of the subject, the blind can be broken by [name] and information will be shared with the medical staff assuming care for the research subject.

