#### **8.1.2 Reporting to the FDA**

The conduct of the study will comply with all FDA safety reporting requirements. It is the responsibility of the Washington University principal investigator to report to the FDA as follows:

- Report any unexpected fatal or life-threatening suspected adverse reaction (refer to Appendix A for definitions) no later than **7 calendar days** after initial receipt of the information.
- Report a suspected adverse reaction that is both serious and unexpected (SUSAR, refer to Appendix A) no later than **15 calendar days** after it is determined that the information qualifies

for reporting. Report an adverse event (refer to Appendix A) as a suspected adverse reaction only if there is evidence to suggest a causal relationship between the drug and the adverse event, such as:

- A single occurrence of an event that is uncommon and known to be strongly associated with drug exposure
- One or more occurrences of an event that is not commonly associated with drug exposure but is otherwise uncommon in the population exposed to the drug
- An aggregate analysis of specific events observed in a clinical trial that indicates those events occur more frequently in the drug treatment group than in a concurrent or historical control group
- Report any findings from epidemiological studies, pooled analysis of multiple studies, or clinical studies that suggest a significant risk in humans exposed to the drug no later than **15 calendar days** after it is determined that the information qualifies for reporting.
- Report any findings from animal or in vitro testing that suggest significant risk in humans exposed to the drug no later than **15 calendar days** after it is determined that the information qualifies for reporting.
- Report any clinically important increase in the rate of a serious suspected adverse reaction of that listed in the protocol or IB within **15 calendar days** after it is determined that the information qualifies for reporting.

Submit each report as an IND safety report in a narrative format or on FDA Form 3500A or in an electronic format that FDA can process, review, and archive.

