## **8.3 Exceptions to Expedited Reporting**

Events that do not require expedited reporting as described in Section 1.1 include:

- planned hospitalizations
- hospitalizations < 24 hours
- respite care
- events related to disease progression

Events that do not require expedited reporting must still be captured in the EDC.

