### **11.1 Adverse Event Collection in the Case Report Forms**

All adverse events that occur beginning with start of treatment must be captured in the AE Form.

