## **APPENDIX A: Definitions for Adverse Event Reporting**

### **A. Adverse Events (AEs)**

As defined in 21 CFR 312.32:

**Definition:** any untoward medical occurrence associated with the use of a drug in humans, whether or not considered drug-related.

**Grading:** the descriptions and grading scales that should be used are those provided by the Department of Health and Human Services' Office for Human Research Protections (OHRP). A copy of this guidance can be found on OHRP's website:

<http://www.hhs.gov/ohrp/policy/advevntguid.html>

**Attribution (relatedness), Expectedness, and Seriousness:** the definitions for the terms listed that should be used are those provided by the Department of Health and Human Services' Office for Human Research Protections (OHRP). A copy of this guidance can be found on OHRP's website:

<http://www.hhs.gov/ohrp/policy/advevntguid.html>

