Table 14.3.1.5	Summary of Related Treatment Emergent Adverse Events	Safety Sample Set
Table 14.3.1.6	Summary of TEAEs Leading to Study Drug Interruption	Safety Sample Set
Table 14.3.1.7	Summary of TEAEs Leading to Study Drug Withdrawn	Safety Sample Set
Table 14.3.2	Summary of Biochemistry Lab Results at Screening	Safety Sample Set

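### Protocol 8.0 and SAP 8.1.1 each require every adverse event to be recorded and then limit tracking to drug-related ones; the related-only sentence should go, with relatedness kept as a recorded attribute.

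*Protocol*

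**What the plan says.** Protocol 8.0 contains two adjacent instructions. The first is "All adverse events must be recorded on the AE tracking case report form (CRF"; the next is "AEs related to study medication only will be tracked". SAP 8.1.1 carries the same pair. All of this is current text, not amendment history.

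Other provisions fall on one side or the other.

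- Every event: Protocol 11.1 says "All adverse events that occur beginning with start of treatment must be captured in the AE Form". Protocol Appendix A defines an adverse event as "any untoward medical occurrence associated with the use of a drug in humans, whether or not considered drug-related". Protocol 8.3 says "Events that do not require expedited reporting must still be captured in the EDC". SAP 3.5 and the opening of SAP section 8 speak of all AEs and SAEs, with no relatedness condition. The officer question in SAP 8.1.1 asks about any unpleasant experience, whether or not the officer thinks it study related.
- Drug-related events: besides the sentence at issue, Protocol 6.0 says "Participants are evaluated from the time of dose administration through 30 days post dose for drug related adverse events".

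The SAP's table index lists a treatment-emergent AE table by system organ class and preferred term (14.3.1.2) and, separately, "Summary of Related Treatment Emergent Adverse Events" (14.3.1.5). Protocol 8.1.2 counts this among the kinds of evidence for a causal link: "An aggregate analysis of specific events observed in a clinical trial that indicates those events occur more frequently in the drug treatment group", relative to a control group.

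**The concern.** Relatedness is an opinion. Protocol 4.0 blinds participants and study team, so whoever forms it does not know the arm. The randomised comparison is the stronger evidence on causality, and it works only if events enter the data whatever anyone thinks caused them.

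Several effects listed in Protocol 7.1.7 (somnolence, dizziness, irritability, poor concentration) are easy to put down to a shift, lost sleep or the range itself. A coordinator who takes the related-only sentence as the collection rule could leave such events off the form. One who follows the sentence before it would enter them. Safety data would then depend on which sentence was followed, and an event never entered may not be recoverable at database lock.

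**Working it through.** **Step 1: can the two sentences be reconciled?** The natural attempt is to read tracked as followed up after recording. Neither document draws that distinction. The form is itself called the AE tracking form, and the same paragraph of Protocol 8.0 uses tracked, without restriction, when it sets the AE time points. As written, the two sentences give opposite instructions.

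**Step 2: which rule do the planned outputs need?**

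- Tables 14.3.1.2 and 14.3.1.5 differ only if unrelated events are in the database. Under related-only tracking they hold the same events.
- The aggregate comparison in Protocol 8.1.2 uses a higher rate on drug than on control as evidence of causality. If events are admitted only after being judged causal, that comparison is circular.

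Both outputs presuppose that all events are collected.

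**Step 3: how much could filtering matter?** The plan gives no AE rate and no share of events judged related, so there is no figure of its own to reproduce. The illustration uses 66 per arm (SAP 2.7), a two-sided Fisher's exact test at 5% with power enumerated over both binomial distributions, and assumed true rates of 30% on ZNS and 10% on placebo.

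- All events kept: 30% v 10%, expected 66 × 0.30 = 19.8 and 66 × 0.10 = 6.6 officers. Difference 20 points, ratio 3, power 78.4%.
- A quarter dropped in each arm: 30 × 0.75 = 22.5% v 10 × 0.75 = 7.5%. Difference 15 points, ratio 3, power 60.9%.
- Half dropped in each arm: 15% v 5%, expected 9.9 and 3.3 officers. Difference 10 points, ratio 3, power 37.5%.
- Five points of background events dropped from each arm: 30 − 5 = 25% v 10 − 5 = 5%, expected 16.5 and 3.3 officers. Difference still 20 points, ratio 5, power 88.7%.

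Proportional dropping shrinks the absolute difference and weakens the signal. Dropping only true background events leaves the difference alone and sharpens it. The documents do not say which would occur.

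**Step 4: rare events.** For an event with an assumed true rate of 2% on ZNS, the chance of seeing at least one among 66 officers is 1 − 0.98^66 = 73.6%. If each event has a 50% chance of being kept, the visible rate is 1% and the chance is 1 − 0.99^66 = 48.5%. Here filtering can only reduce what is seen.

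**The case against.** The strongest reply is that most of the text already requires full capture. The sentence immediately before the disputed one does so, as do Protocol 8.3, 11.1 and Appendix A and SAP 3.5 and section 8. Protocol 8.2 also has secondary sites notify all serious adverse events within one working day, with no relatedness condition. This stands. A reader might infer that the trial will lose its unrelated events; the documents do not support that. Loss follows only where the related-only sentence is taken to govern capture.

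Second, a reader might infer that filtering must understate the drug's effect. Step 3 shows that it need not. SAP section 8 is also descriptive, with no between-arm AE test, so the power figures describe strength of signal and not a planned analysis.

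Third, a reader might infer that the DSMB would be left without sight of cognitive effects. SAP 8.1.1 schedules four cognitive tests at baseline and within 24 hours of dosing and sends the results to the DSMB, along with the number of officers who do not feel safe doing their job. Neither passes through AE attribution. This protection is weaker for somnolence or dizziness, which have no dedicated test.

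Fourth, Protocol 6.0 defines who is evaluable for toxicity and over what window. It is not plainly a collection rule, so a check for consistency is enough there.

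None of these points removes the contradiction between adjacent sentences in both governing documents.

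**Conclusion.** The contradiction is established from the text alone and rests on no assumption: the related-only sentence conflicts with its neighbour in both documents, with at least five other provisions, and with the separate all-event and related-event tables. It should be corrected because it is a stated rule that, if followed, filters safety data on blinded opinion.

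The consequence is conditional on a site following that sentence. Its size cannot be fixed from the documents. Under the assumed rates, power ranges from 37.5% to 89% around an unfiltered 78%, depending on what is dropped; detection of a 2% event falls from 74% to 48% with half-capture. The finding is ambiguity in safety capture, not demonstrated loss of events or a demonstrated bias in one direction.

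**What to change.** - Delete the related-only tracking sentence from Protocol 8.0 and SAP 8.1.1.
- State in both that every adverse event from dosing to 30 days post dose is entered on the AE form, with relatedness as a recorded attribute.
- State that Tables 14.3.1.1 to 14.3.1.4 draw on all such AEs, within each table's own scope (for example, serious events in 14.3.1.3), and that Table 14.3.1.5 draws on the related subset.
- Reconcile the drug-related wording in Protocol 6.0 with this rule.

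This adopts the rule already in Protocol 11.1 and Appendix A. The cost is wording changes in two documents and a few more AE entries per officer. No visit is added.

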### **8.1 Sponsor-Investigator Reporting Requirements**

#### **8.1.1 Reporting to the Human Research Protection Office (HRPO) at Washington University**

Reporting will be conducted in accordance with Washington University IRB Policies.

Pre-approval of all protocol exceptions must be obtained prior to implementing the change.

#### **8.1.2 Reporting to the FDA**

The conduct of the study will comply with all FDA safety reporting requirements. It is the responsibility of the Washington University principal investigator to report to the FDA as follows:

- Report any unexpected fatal or life-threatening suspected adverse reaction (refer to Appendix A for definitions) no later than **7 calendar days** after initial receipt of the information.
- Report a suspected adverse reaction that is both serious and unexpected (SUSAR, refer to Appendix A) no later than **15 calendar days** after it is determined that the information qualifies

for reporting. Report an adverse event (refer to Appendix A) as a suspected adverse reaction only if there is evidence to suggest a causal relationship between the drug and the adverse event, such as:

- A single occurrence of an event that is uncommon and known to be strongly associated with drug exposure
- One or more occurrences of an event that is not commonly associated with drug exposure but is otherwise uncommon in the population exposed to the drug
- An aggregate analysis of specific events observed in a clinical trial that indicates those events occur more frequently in the drug treatment group than in a concurrent or historical control group
- Report any findings from epidemiological studies, pooled analysis of multiple studies, or clinical studies that suggest a significant risk in humans exposed to the drug no later than **15 calendar days** after it is determined that the information qualifies for reporting.
- Report any findings from animal or in vitro testing that suggest significant risk in humans exposed to the drug no later than **15 calendar days** after it is determined that the information qualifies for reporting.
- Report any clinically important increase in the rate of a serious suspected adverse reaction of that listed in the protocol or IB within **15 calendar days** after it is determined that the information qualifies for reporting.

Submit each report as an IND safety report in a narrative format or on FDA Form 3500A or in an electronic format that FDA can process, review, and archive.

Each notification to FDA must bear prominent identification of its contents (“IND Safety Report”) and must be transmitted to the review division in the Center for Drug Evaluation and Research (CDER) or in the Center for Biologics Evaluation and Research (CBER) that has responsibility for review of the IND. Relevant follow-up information to an IND safety report must be submitted as soon as the information is available and must be identified as such (“Follow-up IND Safety Report”).

### **8.1.3 Reporting to Secondary Sites**

The Washington University Sponsor-Investigator will notify the research team at the secondary site of all unanticipated problems involving risks to participants or others that have occurred at other sites within **10 working days** of the occurrence of the event or notification of the Sponsor-Investigator of the event. This includes events that take place both at Washington University and at other site, if applicable.

## **8.2 Secondary Site Reporting Requirements**

The research team at each secondary site is required to promptly notify the Washington University Sponsor-Investigator of all serious adverse events (refer to Appendix A, Section D) within **1 working day** of the occurrence of the event or notification of the secondary site's PI of the event. This notification may take place via email if there is not yet enough information for a formal written report (using FDA Form 3500a (MedWatch) and Washington University's cover sheet (Appendix C). A formal written report must be sent to the Washington University Sponsor-Investigator and designee within **4 calendar days** (for fatal or life-threatening suspected adverse reactions) or **11 calendar days** (for serious unexpected suspected adverse reactions) of the occurrence of the event or notification of the secondary site's PI of the event.

The research team at the secondary site is responsible for following its site's guidelines for reporting applicable events to its site's IRB according to its own institutional guidelines. The research team at Washington University is responsible for reporting all applicable events to the FDA as needed.

Washington University pre-approval of all protocol exceptions must be obtained prior to implementing the change. Local IRB approval must be obtained as per local guidelines. Washington University IRB approval is not required for protocol exceptions occurring at secondary sites.

## **8.3 Exceptions to Expedited Reporting**

Events that do not require expedited reporting as described in Section 1.1 include:

- planned hospitalizations
- hospitalizations < 24 hours
- respite care
- events related to disease progression

Events that do not require expedited reporting must still be captured in the EDC.

## 9.0 STUDY CALENDAR

	VISIT 1 Screening Assessment	VISIT 2 Baseline Assessment	Post-training		
			VISIT 3 Within 5-30 Minutes	VISIT 4 Within 24 Hours	VISIT 5 30 days (+/- 3 days)***
Informed Consent	X				
Demographic Info	X				
Current Meds	X				
Questionnaires	X				X
Cognitive Assessment		X		X	
Clinical ear exam	X	X	X		X
Audiogram	X	X	X		X
ECochG		X			X
DPOAE		X	X		X
WIN		X			X
Sound Measurements	X	X	X		
Randomization			X*		
Oral Dose* ZNS or Placebo			X**		
Blood draw**		X		X	
AE Assessment			X	X	X

\* Dispensed after training if TTS is identified on audiogram 5-30 minutes after shooting.

\*\* Blood draw: Electrolyte panel, BUN, Cr, ALT, and AST; DNA analysis and serum pregnancy test at baseline

\*\*\* If TTS is seen from pure tones after each training session

## 10.0 DATA SUBMISSION SCHEDULE

Case report forms with appropriate source documentation will be completed according to the schedule listed in this section.

Case Report Form	Submission Schedule
Original Consent Form	Prior to study activities
Eligibility Form	At time of consent; Prior to firearm training
Firearm Training Form	Time of firearm training
Adverse Event Form	Continuous

## 11.0 DATA AND SAFETY MONITORING

In compliance with the Washington University Institutional Data and Safety Monitoring Plan, an independent Data and Safety Monitoring Board (DSMB) will be specifically convened for this trial to review toxicity data. A DSMB will consist of no fewer than 3 members including 2 clinical investigators and a biostatistician. Individuals invited to serve

on the DSMB will disclose any potential conflicts of interest to the trial principal investigator and/or appropriate university officials, in accordance with institution policies. Potential conflicts that develop during a trial or a member's tenure on a DSMB must also be disclosed.

The DSM report for the DSMB will be prepared by the study team with assistance from the study statistician, will be reviewed by the DSMB, and will be submitted to the PI. The DSMB must meet at least every six months beginning six months after enrollment of the first participant at the secondary site, no more than one month prior to the due date of the DSM report to the PI. This report will include:

- HRPO protocol number, protocol title, Principal Investigator name, data coordinator name, regulatory coordinator name, and statistician
- Date of initial HRPO approval, date of most recent consent HRPO approval/revision, date of HRPO expiration, date of most recent QA audit, study status, and phase of study
- History of study including summary of substantive amendments; summary of accrual suspensions including start/stop dates and reason; and summary of protocol exceptions, error, or breach of confidentiality including start/stop dates and reason
- Study-wide target accrual and study-wide actual accrual
- Protocol activation date at each participating site
- Average rate of accrual observed in year 1, year 2, and subsequent years at each participating site
- Expected accrual end date, accrual by site, and accrual by cohort
- Objectives of protocol with supporting data and list the number of participants who have met each objective
- Measures of efficacy
- Early stopping rules with supporting data and list the number of participants who have met the early stopping rules
- Power analysis and/or interim analysis (if described in the protocol)
- Summary of toxicities
- Abstract submissions/publications
- Summary of any recent literature that may affect the safety or ethics of the study

The study principal investigator and coordinator will monitor for serious toxicities on an ongoing basis. Once the principal investigator or coordinator becomes aware of an adverse event, the AE will be reported to the HRPO according to institutional guidelines (please refer to Section 1.0).

